## **Week 4**

1. Check to see if any information on participant's contact sheet needs to be updated.
2. Administer the CO test. Refer to the CO directions under the "CO Monitor" section on **Page 8** of this manual. Record the CO.
  - If the CO is 3 or below, you need to administer a urine cotinine test to confirm that the participant is using nicotine products.
3. Collect the participant's Tobacco Use calendar and enter the data for the previous week into the appropriate SPSS database, then return the calendar to the participant.
4. Have the participant fill out all of the questionnaires related to the Session in REDCap, **except the SECOND Minnesota Nicotine Withdrawal scale, and the SECOND Questionnaire of Smoking Urges.**
5. While the participant is filling out the questionnaires on REDCap, have REDCap open on the desktop and double check for participant entry errors as they progress through the questionnaires.
6. Tell the client that you are about to start the recording for their session. Explain that "this is a manualized intervention; therefore it will not feel like traditional therapy. We will be working from a manual and will adhere to the manual content, exclusively."
7. Turn on the recording and **state your name, the date, and the time that you are starting the therapy. Do your best not to say the participant's name while being recorded.**
8. Tell the participant to follow along in their client control workbook as you go through your therapist control manual. Remind them that the counseling could take up to 30 minutes and **they are urged to write down information in their workbooks**

9. **Make sure that you have gone over the Tobacco Use calendar before you finish the recording.** Provide them with copies of the calendar to keep in their pocket/wallet for use when they do not have their manual. Ask that they bring back the calendar and workbook to each visit.
10. After the therapy ask the participant if they have any questions. If they do not, tell them you are ending the recording.
11. Have the participant complete the remaining session measures (Credibility Expectancies Questionnaire, second Minnesota Nicotine Withdrawal Scale, and second Questionnaire of Smoking Urges).
12. Schedule the next appointment for the following week (preferably the same day of the week and same time). **Once you have it scheduled, make sure the appointment is placed in the [name] Lab Google Calendar.**
13. Compensate the participant on their Greenphire ClinCard.
14. Give the participant an appointment card.
15. Upload the session recording to Box.com (MOP, pg. 14) and complete the Audio Recording Length form in REDCap.

## **Week 5**

1. Check to see if any information on participant's contact sheet needs to be updated.
2. Administer the CO test. Refer to the CO directions under the "CO Monitor" section on **Page 8** of this manual. Record the CO level in REDCap.
  - If the CO level is 3 or below, you need to administer a urine cotinine test to confirm that the participant is using nicotine products.
3. Collect the participant's Tobacco Use calendar and enter the data for the previous week into the appropriate SPSS database, then return the calendars to the participant.
4. Have the participant fill out all of the questionnaires related to the session in REDCap, **except the Alliance Questionnaire, SECOND Minnesota Nicotine Withdrawal Scale and the SECOND Questionnaire of Smoking Urges.**
5. While the participant is filling out the questionnaires on REDCap, have REDCap open on the desktop and double check for participant entry errors as they progress through the questionnaires.
6. Tell the client that you are about to start the recording for the session. Explain that "this is a manualized intervention; therefore it will not feel like traditional therapy. We will be working from a manual and will adhere to the manual content, exclusively."
7. Turn on the recording and **state your name, the date, and the time that you are starting the therapy. Do your best not to say the participant's name while being recorded.**
8. Tell the participant to follow along in their client control workbook as you go through your therapist control manual. Remind them that the counseling could take up to 30 minutes and **they are urged to write down information in their workbooks**
9. **Make sure that you have gone over the Tobacco Use and NRT Use calendars before you finish the recording.** Provide them with copies of the calendars to keep in their

pocket/wallet for use when they do not have their manual. Ask that they bring back the calendar and workbook to each visit.

10. When appropriate, pause the audio recording and have the participant fill out the following:
  - **The Alliance Questionnaire**
  - **The second Minnesota Nicotine Withdrawal Scale**
  - **The second Questionnaire of Smoking Urges**
    - **Based on the participant's response to the Minnesota Nicotine Withdrawal Scale and the Questionnaire of Smoking Urges, graph the before and after scores in their workbook.**
11. Un-pause the audio recording and continue the intervention by going over the participant's before and after scores for the Minnesota Nicotine Withdrawal Scale and Questionnaire of Smoking Urges.
12. Review each of the short-acting forms of NRT with the participant. Answer any questions the participant has regarding the medications. Present the medication selection sheet, review it with the participant, and explain that they will be selecting their preferred short-acting NRT to use in conjunction with the patch for the rest of the medication period of the study. Once the participant has made a selection, enter it into REDCap and ask them to write it in their manual.
13. After the therapy, ask the participant if they have any questions. If they do not, tell them you are ending the recording.
14. Schedule the next appointment for the next week (preferably the same day of the week and the same morning time). This appointment should be scheduled with another study staff member other than the therapist who saw the participant for the five weekly sessions. **Once you have it scheduled, make sure the appointment is placed in the [name] Lab Google Calendar.**
15. Give the participant 7 patches. The patches will last through to the next appointment.
16. Give the participant enough of the short-acting NRT they chose to last through to the next appointment.
17. Have the participant sign for the medication in the medication sign-out log.
18. Mark in the Medication Inventory Excel sheet how many of the patches and gum packages/lozenge quit tubes/inhaler cartridges/nasal spray bottles you have given out so that we maintain a running total of prescriptions we have on hand.
19. Remind the participant of the instructions on how to use the patches and gum/lozenges/inhaler/nasal spray and let them know they can reference their workbook if they forget.
20. Make sure to give the participant the slip card.
21. Give the participant a study phone and charger and instruct them to complete the EMA's daily.
22. Compensate the participant on their Greenphire ClinCard.
23. Give the participant an appointment card. **Also, remind them to bring all used and unused patches, patch packets, and short-acting NRT back to the next appointment.**
24. Upload the session recording to Box.com (MOP, pg. 14) and complete the Audio Recording Length form in REDCap.

## Weeks 6, 9 & 13

### Week 6

1. Check to see if any information on participant's contact sheet needs to be updated.
2. Administer the CO test. Refer to the CO directions under the "CO Monitor" section on **Page 8** of this manual. Record the CO level in REDCap.
  - If the CO level is 3 or below, you need to administer a urine cotinine test to confirm that the participant is using nicotine products.
3. Have the participant fill out all of the questionnaires related to the session in REDCap.
4. While the participant is filling out the questionnaires on REDCap, have REDCap open on the desktop and double check for participant entry errors as they progress through the questionnaires.
5. Ask the participant if they experienced any issues in the past week with the short-acting NRT they selected. If they report experiencing issues, follow the discussion guidelines in the therapist manual.
6. If the participant reports issues, determine whether the dosage of the short-acting NRT they selected should be lowered.
7. Remind the participant of the instructions on how to use the patches and gum/lozenges/inhaler/nasal spray and let them know they can reference their workbook if they forget.
8. Ask the participant if they have any questions.
9. Schedule the next appointment in three weeks (preferably the same day of the week and the same morning time). This appointment should be scheduled with another study staff member other than the therapist who saw the participant for the five weekly sessions.

**Once you have it scheduled, make sure the appointment is placed in the [name] Lab Google Calendar.**

10. Give the participant 21 patches. The patches will last through to the next appointment.
11. Give the participant enough of the short-acting NRT they chose to last through to the next appointment.
12. Have the participant sign for the medication in the medication sign-out log.
13. Mark in the Medication Inventory Excel sheet how many of the patches and gum packages/lozenge quit tubes/inhaler cartridges/nasal spray bottles you have given out so that we maintain a running total of prescriptions we have on hand.
14. Compensate the participant on their Greenphire ClinCard.
15. Give the participant an appointment card. **Also, remind them to bring all used and unused patches, patch packets, and short-acting NRT back to the next appointment.**

### Week 9

1. Check to see if any information on participant's contact sheet needs to be updated.
2. Administer the CO test. Refer to the CO directions under the "CO Monitor" section on **Page 8** of this manual. Record the CO level in REDCap.
  - If the CO level is 3 or below, you need to administer a urine cotinine test to confirm that the participant is using nicotine products.
3. Have the participant fill out all of the questionnaires related to the session in REDCap.

4. While the participant is filling out the questionnaires on REDCap, have REDCap open on the desktop and double check for participant entry errors as they progress through the questionnaires.
5. Ask the participant if they experienced any issues in the past three weeks with the short-acting NRT they selected. If they report experiencing issues, follow the discussion guidelines in the therapist manual.
6. If the participant reports issues, determine whether the dosage of the short-acting NRT they selected should be lowered.
7. Remind the participant of the instructions on how to use the patches and gum/lozenges/inhaler/nasal spray and let them know they can reference their workbook if they forget.
8. Discuss the purpose of tapering medication dosage and review tapering instructions.
9. Ask the participant if they have any questions.
10. Schedule the next appointment in a month (preferably the same day of the week and the same morning time). This appointment should be scheduled with another study staff member other than the therapist who saw the participant for the five weekly sessions.

**Once you have it scheduled, make sure the appointment is placed in the [name] Lab Google Calendar.**

11. Give the participant 28 patches (14 14mg patches and 14 7mg patches). The patches will last through to the next appointment. See therapist manual for tapering guidelines.
12. Give the participant enough of the short-acting NRT they chose to last through to the next appointment. See therapist manual for tapering guidelines.
13. Have the participant sign for the medication in the medication sign-out log.
14. Mark in the Medication Inventory Excel sheet how many of the patches and gum packages/lozenge quit tubes/inhaler cartridges/nasal spray bottles you have given out so that we maintain a running total of prescriptions we have on hand.
15. Compensate the participant on their Greenphire ClinCard.
16. Give the participant an appointment card. **Also, remind them to bring all used and unused patches, patch packets, and short-acting NRT back to the next appointment.**
17. Upload the session recording to Box.com (MOP, pg. 14) and complete the Audio Recording Length form in REDCap.

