### **Nicotine Patch**

- Nicotine patches (21, 14, or 7 mg): One box contains 14 patches.
- 21 mg : For participants who self-report smoking *over 10 CPD*
- 14 mg: For participants who self- report smoking *10 or less CPD*
- 7 mg: Lowest-dose patch and dispensed at Week 9

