### Intervention Group A

Week 1:

7 patches (dose based on # of cigarettes smoked per day as reported by subject at Baseline)  
11 blister packs of gum (dose based on if subject reports at Baseline smoking first cigarette within 30 minutes of waking)

Week 2:

7 patches (dose based on # of cigarettes smoked per day as reported by subject at Baseline)  
1 box inhaler and cartridges

Week 3:

7 patches (dose based on # of cigarettes smoked per day as reported by subject at Baseline)  
1 nasal spray bottle

Week 4:

7 patches (dose based on # of cigarettes smoked per day as reported by subject at Baseline)  
2 quit tubes of baseline-indicated lozenge dose, and 1 quit tube of the other dose (for approx. 8-10/day, with both doses to try, e.g., if subject reports at Baseline smoking first cigarette within 30 minutes of awakening, he or she will receive 2 tubes of the 4 mg dose and 1 tube of the 2 mg dose).

Week 5:

7 patches (dose based on # of cigarettes smoked per day as reported by subject at Baseline)  
Participant's selection of short-acting NRT (week long supply)

Week 6:

21 patches (dose based on # of cigarettes smoked per day as reported by subject at Baseline)  
Participant's selection of short-acting NRT (3 week supply)

Week 9:

28 patches  
Participant's selection of short-acting NRT (4 week supply)

\*21 mg participants will begin to taper dose. They will receive 2 weeks' worth of 14 mg patches and 2 weeks' worth of 7 mg patches.

\*\*14 mg participants will receive 4 weeks of 7mg patches.

\*\*Participants using gum or lozenges will taper amount used. They will use half of their original amount for the first two weeks and  $\frac{1}{4}$  of their original amount for the next two weeks.

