### Control Group

Week 1-4: No medication dispensed

Week 5: 7 patches and selected short-acting NRT

Week 6: 21 patches and selected short-acting NRT (3 week supply)

Week 9: 28 patches and selected short-acting NRT (4 week supply)

**If participants using the 21 mg patch report negative side effects, their dose should be adjusted down to the 14 mg patch for patient safety and medication adherence.**

**If participants using the 4mg gum report negative side effects, their dose should be adjusted down to the 2mg gum for patient safety and medication adherence.**

**If participants using the 4 mg lozenge report negative side effects, their dose should be adjusted down to the 2 mg lozenge for patient safety and medication adherence.**

**If participants using the 4mg dosing instructions for the inhaler report negative side effects, their dose should be adjusted down to the 2mg dosing instructions for patient safety and medication adherence.**

**Participants must sign the Medication Sign-Out Log when receiving medications. Research staff must initial the form and must also log the medication in the Medication Inventory Database.**

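### The Week 9 dispensing step gives every participant the 21 mg patch taper, which contradicts the written rule for 14 mg participants in Intervention Groups A to D

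*Protocol*

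**What the plan says.** **Week 9 visit (Protocol, Weeks 6, 9 & 13, Week 9, step 11).** The instruction is "Give the participant 28 patches (14 14mg patches and 14 7mg patches". This part of the manual serves all arms, and the step sets no condition on the patch strength in use. It then refers staff to the therapist manual for tapering guidance; that manual is not among the documents. Step 8 of the same visit has staff explain tapering to the participant.

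**Medication Dispensing, Intervention Groups A to D, Week 9.** The total is 28 patches, with two notes repeated in each of the four groups. For 21 mg participants: "They will receive 2 weeks' worth of 14 mg patches and 2 weeks' worth of 7 mg patches". For the others: "14 mg participants will receive 4 weeks of 7mg patches".

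**Medication Dispensing, Control Group.** The entry is "Week 9: 28 patches and selected short-acting NRT (4 week supply"), with no split by strength.

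**Who is on 14 mg.** The Nicotine Patch section assigns that strength with "14 mg: For participants who self- report smoking" 10 or fewer cigarettes per day. A second route follows the Control entry: "If participants using the 21 mg patch report negative side effects, their dose should be adjusted down to the 14 mg patch". The Nicotine Patch section also notes "7 mg: Lowest-dose patch and dispensed at Week 9", without limiting this to one arm.

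**The concern.** A staff member working through the Week 9 checklist would hand out one fixed set of strengths. That set is correct for someone coming off 21 mg. Someone coming off 14 mg would get two more weeks at the strength already in use, at the very visit where tapering is explained. The same participant would get 7 mg patches only if staff turned to the group's dispensing page. Two staff members could therefore supply the same participant differently, and each would be following the manual.

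What is at stake is the dose and the timing of the taper between Weeks 9 and 13. Both rules hand over the same number of patches, so a simple inventory count would not reveal which one was followed.

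**Working it through.** **Inputs.** Step 11: 14 patches of 14 mg and 14 of 7 mg. Dispensing notes, Groups A to D: for 21 mg, two weeks of 14 mg and two of 7 mg; for 14 mg, four weeks of 7 mg. Box size, from the Nicotine Patch section: "One box contains 14 patches". I assume one patch per day.

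**Reproducing step 11.** The 21 mg note gives 2 × 7 = 14 patches of 14 mg plus 2 × 7 = 14 patches of 7 mg, a total of 28. This is exactly the split in step 11. The 14 mg note gives 4 × 7 = 28 patches of 7 mg and none of 14 mg. A participant cannot be supplied under both.

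**A 14 mg participant in Groups A to D, Weeks 9 to 13.**

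| | Step 11 | Dispensing note |
|---|---|---|
| Patches | 14 + 14 = 28 | 28 |
| Nominal total | 14 × 14 + 14 × 7 = 294 mg | 28 × 7 = 196 mg |
| Days at 14 mg | 14 | 0 |
| Days at 7 mg | 14 | 28 |
| Dose change at Week 9 | 14 to 14 mg: 1 − 14/14 = 0% | 14 to 7 mg: 1 − 7/14 = 50% lower |
| Boxes of 14 | 1 + 1 = 2 | 28/14 = 2 |

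The difference is 294 − 196 = 98 mg, a ratio of 294/196 = 1.5, and 14 of the 28 patches differ in strength. For comparison, a 21 mg participant drops by 1 − 14/21 = 33% at Week 9 under either text. Under step 11 the 14 mg participant still moves to 7 mg, two weeks later, and still finishes on 7 mg.

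**Effect on the analysis.** The SAP (Aim 3) can treat adherence as doses taken divided by doses given. For patches, the doses given at Week 9 are 28 under both rules, so the denominator does not move.

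**Who could be affected.** Under the protocol's Inclusion Criteria entry requires at least 10 cigarettes per day, and the 14 mg patch is for 10 or fewer; the overlap is exactly 10. The SAP's Inclusion Criteria set the floor at 5, with the same 14 mg cut-off, so the overlap would be 5 to 10. Neither document gives the number of participants in either range.

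**Control.** The dispensing entry names no strengths at Week 9, so nothing there contradicts step 11. The Nicotine Patch section sets starting strengths and says 7 mg is dispensed at Week 9, but gives no split. Step 11 is therefore the only written Week 9 split by strength for that arm, and it provides no taper from 14 mg.

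**The case against.** The strongest reply is that the dose-specific taper is already written for all four intervention groups, and that step 11 is a checklist line showing the usual 21 mg case and sending staff elsewhere for the taper. This is a plausible account of how the line came about. It does not remove the conflict, because step 11 names strengths. The Week 6 step in the same shared section gives only a count of 21 patches and leaves strength to the dispensing pages. Where the manual intends a choice, as in the weekly intervention sessions, it writes out both strengths.

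The reply does limit what may be concluded. A reader might infer that 14 mg participants were in fact supplied wrongly. The documents do not show this: the therapist manual is not available and practice is unknown. Four other inferences also go too far:

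- **A lost taper or an overdose.** Under step 11 the move from 14 to 7 mg still happens, and no strength exceeds the one already in use.
- **A contradiction in Control.** That arm has no second Week 9 split for step 11 to contradict.
- **Participants stepped down from 21 mg are part of the conflict.** In Groups A to D, patch dose through Week 6 is tied to baseline smoking, and the manual does not say whether a stepped-down participant counts as a 14 mg participant for the taper. If not, their written taper equals step 11 and nothing conflicts.
- **Few are affected.** The protocol's floor of 10 suggests so, but the SAP's floor of 5 would admit more.

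**Conclusion.** The point holds as a conflict between two operative dispensing instructions, limited to 14 mg participants in Intervention Groups A to D. Followed literally, step 11 delays their step from 14 to 7 mg by two weeks, with 98 mg more nominal patch strength over 28 days. In Control the problem is a gap: no Week 9 taper from 14 mg is written for that arm.

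Severity is minor. The patch count, the adherence denominator and the primary outcomes are unchanged. The size rests on one patch per day and on nominal strength, and it is per participant; no total can be given because the number on 14 mg is unknown. The conclusion concerns the written rule only.

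**What to change.** Make step 11 conditional on the patch dose, in all arms: participants on 21 mg receive 14 patches of 14 mg, then 14 of 7 mg; participants on 14 mg receive 28 patches of 7 mg. Put the same two lines in the Control Group dispensing entry.

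Separately, ask the investigator to state which taper applies to someone stepped down from 21 mg to 14 mg for side effects. That is a clarification the manual needs, and the answer is a dosing decision.

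If the Medication Given form or the Medication Sign-Out Log records strength at Week 9, tabulate the strengths dispensed by arm; this would show which rule was followed. The protocol says the form captures patch dosage, but its options are not shown, and it may not hold a mixed 14 mg and 7 mg supply.

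The cost is one conditional sentence, two lines in the Control entry, one question to the investigator and, if the records allow, one table.

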## **Week 13**

1. Check to see if any information on participant's contact sheet needs to be updated.
2. Administer the CO test. Refer to the CO directions under the "CO Monitor" section on **Page 8** of this manual. Record the CO level in REDCap.
  - If the CO level is 3 or below, you need to administer a urine cotinine test to confirm that the participant is using nicotine products.
3. **Collect the study phone and charger given to the participant.**
4. Have the participant fill out all of the questionnaires related to the session in REDCap.
5. While the participant is filling out the questionnaires on REDCap, have REDCap open on the desktop and double check for participant entry errors as they progress through the questionnaires.

6. Schedule the next appointment in a month (preferably the same day of the week and the same morning time). This appointment should be scheduled with another study staff member other than the therapist who saw the participant for the five weekly sessions.  
